Written instructions on commercially-available packages are insufficient to ensure comprehension and correct dosing. Over 98% of over-the-counter liquid medications are inconsistent with regard to dosing directions and markings on the dosing device.⁷ Dosing cups, often dispensed with such medications, are associated with an increased risk of making a large dosing error when compared to an oral syringe.⁸ Plain-language, pictogram-based interventions with teach-back have shown promise in improving dosing accuracy in the pediatric ED⁹, but have not become a routine part of discharge teaching. In particular, a combination of improved teaching and provision of a dosing syringe is associated with a significantly decreased risk of error (adjusted OR 0.3, 95%CI 0.1-0.7).¹⁰ Improved written materials may also have potential to improve provider counseling and teaching around medication use.¹¹ Our pilot work demonstrates that ED parents perceive a need for dosing demonstration,¹² and are open to teach-back techniques to confirm their understanding.¹³

RESEARCH DESIGN AND METHODS

Briefly describe study design and anticipated enrollment, i.e., number of subjects to be enrolled by researchers study-wide and by Partners researchers. Provide a brief summary of the eligibility criteria (for example, age range, gender, medical condition). Include any local site restrictions, for example, “Enrollment at Partners will be limited to adults although the sponsor’s protocol is open to both children and adults.”

We plan a randomized controlled trial of an intervention to improve ED discharge teaching. We plan to approach 400 parents, with a goal sample size of 200 parents. Parents will be approached for consent, and randomized after consent

We will enroll parents of children between ages of 90 days to 11.9 years, who are being discharged with a plan for use of liquid acetaminophen (any age) or ibuprofen (limited to those >6 months old). The clinical team will determine planned medication use. Inclusion criteria include parental fluency in English or Spanish, ability to be reached by telephone over the next 7 days and planned discharge home. Exclusion criteria include presence of a complex chronic condition¹⁴ in the child and planned use of a non-standard weight-based medication dose. Adults who are not the parent or legal guardian of the child they are with in the ED will also be excluded.

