Follow-up. Participants will be called at 48-72 hours to assess dosing knowledge (primary outcome), comfort with home care and encounters with other care providers; and at 5-7 days to assess persistence of knowledge. Participants will be asked during enrollment about their preferred time of day for follow-up calls. If they do not answer at the time of the follow-up call, they will sent a text message in their preferred language (Spanish or English) to arrange a time for follow-up. Parents will be allowed to refer to the information sheet at the time of assessment.

For studies involving treatment or diagnosis, provide information about standard of care at Partners (e.g., BWH, MGH) and indicate how the study procedures differ from standard care. Provide information on available alternative treatments, procedures, or methods of diagnosis.

Participants will receive standard ED teaching or standard ED teaching + intervention, and so no participant will receive less than the existing standard of care.

Describe how risks to subjects are minimized, for example, by using procedures which are consistent with sound research design and which do not unnecessarily expose subjects to risk or by using procedures already being performed on the subject for diagnostic or treatment purposes.

The primary risks to subjects are minimized as below:

1. Confusion about Instructions: We feel this is less likely because the intervention is based on strategies, such as teach-back techniques, that confirm understanding

prior to discharge. All participating families will have the usual care discharge, and intervention families will have additional teaching. Fidelity of the RAs to the intervention will be monitored closely. Parents will be offered the opportunity to speak to their treating provider if they have any questions that the RA is unable to answer. Parental conversations with the treating provider following the intervention delivery will be observed and abstracted by the RA.

2. **Privacy Breach:** The risk of loss of confidentiality will be minimized by keeping all data in a locked cabinet in a locked office, on a secure research drive or in REDCap. All study staff will undergo CITI training in human subjects research and privacy protection. Demographic information collection and intervention delivery will be conducted in a private room. All privacy breaches will be reported to the IRB in accordance with MGH regulations.

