The intervention teaching may improve parental understanding of safe medication dosing for their children at home. The overall study will add to our knowledge about how to safely communicate complex concepts to parents at the time of ED discharge.

EQUITABLE SELECTION OF SUBJECTS

The risks and benefits of the research must be fairly distributed among the populations that stand to benefit from it. No group of persons, for example, men, women, pregnant women, children, and minorities, should be categorically excluded from the research without a good scientific or ethical reason to do so. Please provide the basis for concluding that the study population is representative of the population that stands to potentially benefit from this research.

We will enroll parents of children between ages of 90 days to 11.9 years, who are being discharged with a plan for use of liquid acetaminophen (any age) or ibuprofen (limited to those >6 months old). This will include parents from all racial and ethnic groups who speak either English or Spanish.

When people who do not speak English are excluded from participation in the research, provide the scientific rationale for doing so. Individuals who do not speak English should not be denied participation in research simply because it is inconvenient to translate the consent form in different languages and to have an interpreter present.

We will be enrolling parents who speak English and Spanish.

For guidance, refer to the following Partners policy:

Obtaining and Documenting Informed Consent of Subjects who do not Speak English
https://partnershealthcare-public.sharepoint.com/ClinicalResearch/Non-English_Speaking_Subjects.1.10.pdf

RECRUITMENT PROCEDURES

Explain in detail the specific methodology that will be used to recruit subjects. Specifically address how, when, where and by whom subjects will be identified and approached about participation. Include any specific recruitment methods used to enhance recruitment of women and minorities.

Recruitment methods Parents will be enrolled from the MGH ED by trained research assistants (RAs). RAs routinely screen for eligible patients for a variety of studies in our ED. Consenting participants will be randomized to intervention vs. usual care. The intervention will be delivered by RAs who have been trained by the PI ([name]) and the ED pharmacist ([name]).

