Provide details of remuneration, when applicable. Even when subjects may derive medical benefit from participation, it is often the case that extra hospital visits, meals at the hospital, parking fees or other inconveniences will result in additional out-of-pocket expenses related to study participation. Investigators may wish to consider providing reimbursement for such expenses when funding is available

We plan to provide a single payment of \$20 to the participant by mailed CVS gift card after completion of the first follow-up interview, and not to collect SSN/ITIN numbers. We are particularly interested in enrolling participants with limited health literacy and limited English proficiency, and therefore anticipate that many of our participants may be undocumented or be uncomfortable providing a social security number. This is a one-time acknowledgement of participant time and effort, not a repeating payment.

For guidance, refer to the following Partners policies:

Recruitment of Research Subjects

https://partnershealthcare-public.sharepoint.com/ClinicalResearch/Recruitment_Of_Research_Subjects.pdf

Guidelines for Advertisements for Recruiting Subjects

https://partnershealthcare-public.sharepoint.com/ClinicalResearch/Guidelines_For_Advertisements.1.11.pdf

Remuneration for Research Subjects

https://partnershealthcare-public.sharepoint.com/ClinicalResearch/Remuneration_for_Research_Subjects.pdf

CONSENT PROCEDURES

Explain in detail how, when, where, and by whom consent is obtained, and the timing of consent (i.e., how long subjects will be given to consider participation). For most studies involving more than minimal risk and all studies involving investigational drugs/devices, a licensed physician investigator must obtain informed consent. When subjects are to be enrolled from among the investigators' own patients, describe how the potential for coercion will be avoided.

Parents will give informed consent for participation.

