The risk of loss of confidentiality will be minimized by keeping all data in a locked cabinet in a locked office, on a secure research drive or in REDCap. All study staff will undergo CITI training in human subjects research and privacy protection. Demographic information collection and intervention delivery will be conducted in a private room. All privacy breaches will be reported to the IRB in accordance with MGH regulations.

SENDING SPECIMENS/DATA TO RESEARCH COLLABORATORS OUTSIDE PARTNERS

Specimens or data collected by Partners investigators will be sent to research collaborators outside Partners, indicate to whom specimens/data will be sent, what information will be sent, and whether the specimens/data will contain identifiers that could be used by the outside collaborators to link the specimens/data to individual subjects.

N/A

Specifically address whether specimens/data will be stored at collaborating sites outside Partners for future use not described in the protocol. Include whether subjects can withdraw their specimens/data, and how they would do so. When appropriate, submit documentation of IRB approval from the recipient institution.

N/A

RECEIVING SPECIMENS/DATA FROM RESEARCH COLLABORATORS OUTSIDE PARTNERS

When specimens or data collected by research collaborators outside Partners will be sent to Partners investigators, indicate from where the specimens/data will be obtained and whether the specimens/data will contain identifiers that could be used by Partners investigators to link the specimens/data to individual subjects. When appropriate, submit documentation of IRB approval and a copy of the IRB-approved consent form from the institution where the specimens/data were collected.

Biostatistical analysis

Primary analyses will be based on intention-to-treat. Data will be stored in REDCap and analyzed in STATA. We will evaluate:

- Study process variables Descriptive statistics will be used to delineate the number screened, eligible, approached, assented/consented and randomized. Reviewer checklists will be used to determine adherence. Duration of discharge process will be recorded for all participants to address questions about feasibility. We will also record number of teach-back cycles required. We will compare retention to follow-up call between intervention and control groups using a Mantel-Haenszel analysis.

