- Outcomes The primary outcome is safe dosing (defined as within 20% range of the weight-based dose) at the 48-72 hour follow-up call. A 20% range has been used in prior studies,^{9,10} and we have successfully completed telephone assessment of dose accuracy in previous work.^{4,5} We will use logistic regression models to compare differences between study groups. The secondary outcomes (including parental comfort, encounters with other providers and persistence of dosing knowledge) will be used for hypothesis generation.
- Missing data. We will do a sensitivity analysis to test varied assumptions about missing data based on previously reported rates of dosing error following ED visits,^{5,9} or multiple imputation depending on the number of patients with missing data.
- Exploratory subgroup analysis: We will examine: 1) intervention effect in English-speakers as compared to Spanish-speakers, 2) effect size by health literacy, and 3) the intervention efficacy in those receiving both acetaminophen and ibuprofen education as compared to those receiving single-medication education 4) differential risk of overdose error as compared to underdose error

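### The randomisation method and any strata are not specified and the primary model names no covariates, so a chance imbalance in language could go uncorrected; the likely effect is small and the remedy is cheap

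*Combined protocol and SAP*

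**What the plan says.** Allocation is described in two places. Research Design and Methods gives the timing: "Parents will be approached for consent, and randomized after consent". Recruitment Procedures gives the arms: "Consenting participants will be randomized to intervention vs. usual care". The target is a "goal sample size of 200 parents". The supplied text states no allocation ratio, sequence generation, block size, stratification factor or concealment.

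The Biostatistical analysis section compares the arms on safe dosing at 48-72 hours by logistic regression and names no covariates. Its exploratory subgroup list includes "intervention effect in English-speakers as compared to Spanish-speakers" and "the intervention efficacy in those receiving both acetaminophen and ibuprofen education as compared to those receiving single-medication education", along with health literacy. Retention to the follow-up call is to be compared "between intervention and control groups using a Mantel-Haenszel analysis", with no stratifying variable named.

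Two other places bear on language. Background and Significance says that misunderstanding of dosing instructions is a particular problem for families with limited health literacy and limited English proficiency. The remuneration text under Recruitment Procedures says: "We are particularly interested in enrolling participants with limited health literacy and limited English proficiency". The share of parents expected to prefer Spanish is not given anywhere.

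**The concern.** The plan itself treats language as related to dosing misunderstanding, so language is a plausible predictor of the primary outcome. If allocation is simple and the primary model has only the arm term, nothing in the design or analysis would correct an uneven split of Spanish-preferring parents. Such a split would shift the observed arm difference in that one trial and would slightly reduce the precision of the language subgroup.

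Both language and the planned drug(s) can be known before allocation. Fluency in English or Spanish is an eligibility criterion, and the clinical team sets the medication plan. They are therefore usable as strata and as covariates.

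A smaller point concerns definition. A parent fluent in both languages belongs to both groups as subgroup 1 is worded. The follow-up procedure already works with each parent's preferred language, since a parent who misses a call is sent a "text message in their preferred language (Spanish or English").

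**Working it through.** The plan gives no figure on this point, so there is nothing of its own to reproduce.

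**Inputs.**
- From the documents: 200 parents, two arms, and an adjusted odds ratio for error of 0.3 cited in Background and Significance.
- Assumptions: 100 parents per arm; 15%, 25% or 35% preferring Spanish (S = 30, 50 or 70); a 20-point difference in error rate between language groups; and a 50% error rate under usual care. Applying the odds ratio of 0.3 to 50% (odds of 1) gives 0.3/1.3 = 23.1% under the intervention.

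**Step 1. Chance of a 10-point imbalance.** Let X be the number of Spanish-preferring parents in one arm. With unstratified allocation and fixed totals of 100:100, X is hypergeometric (200 parents, S Spanish-preferring, 100 drawn). The arms differ in Spanish share by (2X - S)/100. A difference of 10 points or more means X ≥ (S + 10)/2 or the mirror image.

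| S | Split at the threshold | Two-sided probability |
|---|---|---|
| 30 | 20 v 10 | 7.3% |
| 50 | 30 v 20 | 14.1% |
| 70 | 40 v 30 | 18.2% |

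**Step 2. Shift in the unadjusted arm difference.** The shift is the imbalance in share times the gap in error rate. At a 10-point imbalance it is 0.10 × 0.20 = 0.02, or 2 points.

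For a typical imbalance, take one standard deviation. Var(X) = 100 × p(1 - p) × 100/199 with p = S/200, and the SD of the share difference is 2 × SD(X)/100.
- S = 30: SD(X) = 2.53, share SD = 5.1 points, shift = 1.0 point.
- S = 50: SD(X) = 3.07, share SD = 6.1 points, shift = 1.2 points.
- S = 70: SD(X) = 3.38, share SD = 6.8 points, shift = 1.4 points.

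For scale, the standard error of the arm difference at 100 per arm is sqrt(0.5 × 0.5/100 + 0.231 × 0.769/100) = 0.065, or 6.5 points.

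**Step 3. Precision in the Spanish-preferring subgroup (S = 50).** The half-width is 1.96 × sqrt(0.25/n₁ + 0.1776/n₂), with n₁ under usual care and n₂ under intervention.
- 25 v 25: 25.6 points.
- 30 v 20: 25.7 points.
- 20 v 30: 26.6 points.

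The uneven split costs 0.1 to 1.0 points on an interval that is already about ±26. Subgroup size is the limit, and stratifying does not change that.

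**Step 4. Mantel-Haenszel with one stratum.** The statistic equals (N - 1)/N times Pearson's chi-square. For an illustrative retention of 85/100 v 75/100, Pearson gives 3.125 and Mantel-Haenszel gives 199/200 × 3.125 = 3.109. The test is valid without strata.

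**The case against.** The strongest objection is that the harm is slight. Randomisation makes the comparison unbiased on average, and the ordinary standard error already allows for chance imbalance. A typical shift of about 1 point is small against a standard error of 6.5 points. Adding language to the logistic model would deal with the imbalance in the primary comparison without touching allocation. All of this stands, and it sets the weight of the point.

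The document is also a protocol summary that cites a separate detailed protocol, which was not supplied. A reader might infer from the silence that randomisation is unstratified. The text does not say so. The detailed protocol is cited for safety and adverse-event procedures, and whether it covers allocation is unknown. The supportable finding is that the method is not specified here.

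Other stronger readings also lack support:
- A reader might take language and number of drugs as declared effect modifiers. They are listed as exploratory subgroups, and the background text concerns risk of misunderstanding, not a different intervention effect.
- A reader might assume that the Spanish-speaking group is small. No share is given, and the stated interest is in enrolling parents with limited English proficiency.
- A reader might think that the Mantel-Haenszel analysis fails without randomisation strata. It concerns retention only, can use any baseline variable as its strata, and remains valid with one stratum.

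Health literacy is also a listed subgroup and has as good a claim to be prognostic. Leaving it out of the strata is a matter of keeping the number of cells low; it can enter the model as a covariate.

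**Conclusion.** The point holds as a modest, low-cost improvement. The supplied text specifies neither a randomisation method nor strata, and the primary model as stated contains no baseline covariate, although the plan connects language with dosing misunderstanding and intends to compare effects by language and by one versus two drugs.

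If allocation is simple and the model unadjusted, the chance of a 10-point or larger imbalance in Spanish share is 7% to 18%, for an assumed share of 15% to 35%. The typical effect on the arm difference is about 1 point, and 2 points at a 10-point imbalance, if error rates differ by 20 points between language groups. There is no bias on average, and the validity of the primary analysis is not in question. The figures rest on the assumed Spanish share, the assumed 20-point gap and 100 parents per arm, none of which the documents state.

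**What to change.** 1. State the randomisation method. Record preferred language (English or Spanish) and planned drug(s) (one or both) before allocation. Then use permuted blocks of varying size, stratified by these two factors, with the next assignment concealed from the research assistant until consent and both items are entered. Two binary factors give four strata, which is workable with 200 parents.
2. Include both factors as covariates in the primary logistic model.
3. Define subgroup 1 by preferred language, so that each bilingual parent falls in one group. Define subgroup 3 by the drug(s) planned before allocation, since the present wording refers to education received.
4. Optionally, use the same two factors as the Mantel-Haenszel strata for retention.

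If enrolment has begun, leave allocation as it is and make only the analysis changes. If the detailed protocol already sets out the allocation method, cite it and align the model with it.

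The cost is one allocation list with four strata, two items entered before allocation, and a few sentences in the Biostatistical analysis section. No extra participants, visits or staff are needed.
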